8.4 Secondary Objectives

The secondary objectives are to evaluate the time to development of worst grade 3 HFSR toxicity, proportion of all grades of hypertension, proportion of all grade toxicities and progression-free survival. All toxicities will be evaluated using CTCAE v4.03.

8.4.1 Time to worst grade 3 HFSR toxicity

Time to worst grade 3 HFSR toxicity is defined as the time (days) from start date of study drug to date of first documented grade 3 HFSR toxicity and will be calculated only for patients who had a HFSR toxicity grade 3.

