1.5 Rationale for Use in Colorectal Cancer

The intended outcome of successfully and significantly mitigating regorafenib-induced HFSR is that patients will be able to stay on the regorafenib for a longer period to increase efficacy. The hypothesis underlying this trial is that the co-administration of perindopril with regorafenib will mitigate HFSR symptoms.

This may not be the case, and if the HFSR is more severe with the addition of perindopril than with regorafenib alone, the study will be discontinued.

As a secondary endpoint, hypertension will also be followed.

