1.6 Clinical experience with Regorafenib

47% of regorafenib treated patients in the CORRECT trial experienced HFSR of all grades, while 17% experienced grade 3 HFSR. Results of the CONCUR Trial were similar. Although 74.3% of patients experienced any grade of HFSR, 16.2% experienced grade 3.

All efforts need to be made to find new therapeutic combinations to reduce HFSR, as it causes a significant decrease in a patient's quality-of-life.

Expected time on trial: In the CORRECT trial (regorafenib versus placebo) overall survival was 6.4 vs 5.0 months (HR=0.77, p=0.0052) and PFS was 1.9 vs 1.7 months (HR=0.49, p<0.000001). In the CONCUR trial, (regorafenib versus placebo) overall survival was 8.8 versus 6.3 months (HR=0.550, 95% CI 0.395-765, p=0.0002 (I sided). PFS was 3.2 versus 1.7 months (HR=0.311, 95% CI 0.222-0.435, p<0.0001 (1 sided)).

Based on CONCUR, expected time patients will stay on trial is four months.

2. Study objectives

This trial will measure the incidence and severity of HFSR and hypertension in patients receiving both perindopril and regorafenib.

The incidence of HFSR will be expressed as the number of patients out of study (N=34) who are experiencing HFSR of all grades. Severity will be evaluated using CTCAE v4.03 criteria.

The incidence of hypertension will be expressed as the number of patients on study (N=34) who are experiencing hypertension of all grades. Severity will be evaluated using CTCAE v4.03 criteria.

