2.2 Secondary outcomes

- Hypertension: All grades of hypertension will be evaluated using CTCAE v4.03, weekly for the first six weeks while they are on the study drug, then every second week and during the 30-day follow up period (Post therapy)(see attached study schedule, APPENDIX A).

Phase II Study of Perindopril and Regorafenib in mCRC (PARICCA)

- Toxicity: all grades of AE including HFSR will be evaluated using CTCAE v4.03, at baseline and at D1 of each cycle while they are on the study drug and during the 30-day follow up period (Post therapy).
- Time course to development of worst grade (grade 3) HFSR.
- PFS will be evaluated based on RECIST v1.1 criteria, 20% progression or any new lesion.

3. Investigators and other study participants

Study sponsors and PIs:

[name], [name]
BC Cancer Agency – Vancouver Cancer Centre
[name]
[name]

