5.2 Withdrawal of subjects from study

Patients will remain on trial and will receive regorafenib and perindopril until clinical radiological disease progression, based on RECIST v1.1 criteria. If patients progress on regorafenib, both drugs will be stopped. However, after the patient progresses (i.e. is no longer on trial) the medication can be continued if the investigator feels that there is a clinical benefit.

A subject may discontinue participation in this study at any time at the investigator's discretion or at the request of the subject.

If a subject discontinues before treatment starts (Cycle 1, day 1) she/he is not required to complete end of study assessments.

If a subject discontinues after receiving treatment for any reason, the investigator should make every effort to complete end of study assessment and the one month follow-up assessments of concomitant medications and adverse events.

Any occurrence of death, and any excluded medications taken after study withdrawal should be documented in the CRF and source documents.

Subjects withdrawn from the study retain their subject number, if already given. New subjects will be allocated a new subject number.

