5.2.1 Withdrawal of subjects from study treatment

Subjects *must* be withdrawn from study treatment for the following reasons:

- At their own request or at the request of their legally acceptable representative.
- At any time during study treatment and without giving reasons, a subject may decline to participate further. The subject will not suffer any disadvantage as a result.
- If, in the investigator's opinion, continuation of study treatment would be harmful to the subject's well-being.
- Severe allergic reactions, such as exfoliate erythroderma, anaphylaxis, or vascular collapse.
- Any other potential adverse reaction deemed sufficiently serious to warrant discontinuation of treatment by the Investigator.
- Substantial non-compliance with study procedures.
- Patients with a b-HCG test consistent with pregnancy. Pregnancy will be reported along the same timelines as a serious adverse event (see Section 7.5.2).
- Use of illicit drugs or other substances that may, in the opinion of the Investigator or a designated associate(s), have a reasonable chance of contributing to toxicity or otherwise confound the results.
- Any hemorrhage or bleeding event > CTCAE Grade 3 within 4 weeks of start of study medication.

Phase II Study of Perindopril and Regorafenib in mCRC (PARICCA)

- Development of any intercurrent illness or situation which would, in the judgment of the Investigator, may affect assessments of clinical status and study endpoints to a relevant degree.
- Patients should come off study treatment for disease progression. If the treating physician feels that the patient will receive clinical benefit from continued study treatment despite progression, the patient may remain on study drug. However, the patient will be considered as having progressive disease, as per the RECIST criteria, version 1.1.
- The development of a second malignancy.
- Patient lost to follow up.
- Interruption of study drug is longer than 28 consecutive days (including the 1 week break in each cycle).
- More than two dose reductions of the study drug are necessary.
- Death.

A subject who is terminated from the study after signing the informed consent but before starting the drug is regarded as a “screening failure”.

Any subject removed from study treatment will remain under medical supervision until discharge or transfer is medically acceptable.

In all cases, the reason for withdrawal must be recorded in the CRF and in the subject's medical records.

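### Time to Grade 3 HFSR is calculated only in patients who develop it, so it cannot show how Grade 3 risk builds up over time in all treated patients (minor; cheap to improve)

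*Combined protocol and SAP*

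**What the plan says.** Section 2.2 lists the secondary outcome as "Time course to development of worst grade (grade 3) HFSR", and section 8.4 restates the aim as to "evaluate the time to development of worst grade 3 HFSR toxicity". Section 8.4.1 gives the measure: it is "defined as the time (days) from start date of study drug to date of first documented grade 3 HFSR toxicity", and it "will be calculated only for patients who had a HFSR toxicity grade 3".

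Section 8.4.1 gives no rule for patients without the event, no competing-event rule and no summary statistic. Section 8.4.2, directly after it, gives PFS a censoring rule, Kaplan-Meier curves, and a median with a 95% confidence interval.

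Three other provisions bear on the point:
- Section 8.3.2 separately plans the proportion with Grade 3 HFSR and its 95% confidence interval.
- Sections 7.1.2.4, 7.1.2.5 and 8.5 run adverse-event recording to 30 days after the last dose.
- Section 5.2 says "If patients progress on regorafenib, both drugs will be stopped", but section 5.2.1 allows that, where the physician sees benefit, "the patient may remain on study drug".

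**The concern.** Restricting the calculation to patients who had the event selects on something that happens after baseline. The trial hypothesis is that perindopril mitigates HFSR. A patient in whom Grade 3 is prevented leaves the calculation instead of lengthening it. If perindopril prevented half of the Grade 3 cases and left the timing of the rest alone, the expected event-only distribution would not change at all, whatever the shape of the hazard.

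The times are also truncated: an onset that would have come after the end of recording is never seen. How much is lost depends on how long patients stay on drug. Section 1.5 hopes that "patients will be able to stay on the regorafenib for a longer period to increase efficacy", so a change in treatment duration is foreseeable.

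At stake is how a secondary result is read. A protective effect could leave the reported time almost unchanged, and longer treatment could lengthen it with no effect on HFSR.

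**Working it through.** **Inputs.** From the documents: Grade 3 HFSR 17% in CORRECT (1.2, 1.6); median PFS 1.9 months in CORRECT ("PFS was 1.9 vs 1.7 months") and 3.2 months in CONCUR (1.6); expected time on trial four months (1.6); N=34 (8.7). Assumed: PFS stands in for time on treatment; 30.4375 days per month; the hazard shapes below.

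**Plan's own figure.** The plan states none for this endpoint. Its N reproduces: [(1.960·√(0.47·0.53) + 0.842·√(0.24·0.76)) / 0.23]² = 33.8, so 34.

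**Patients contributing.**
- At 17%: 34 × 0.17 = 5.8 (95% binomial range 2 to 10); P(2 or fewer) = 0.056.
- At half that proportion: 34 × 0.085 = 2.9; P(2 or fewer) = 0.439.

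**Constant hazards.** Let L be the HFSR hazard and M the hazard of leaving observation. Time given an event is exponential with rate L+M, so its median is ln2/(L+M), and the eventual incidence is L/(L+M). The 30-day window is left out at this step. With M = ln2/(1.9 × 30.4375) = 0.01199 per day and L = M × 0.17/0.83 = 0.00245 per day:

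| Scenario | L+M per day | Event-only median | Incidence |
|---|---|---|---|
| Base | 0.01444 | 48.0 days | 17.0% |
| HFSR hazard halved | 0.01321 | 52.5 days | 9.3% |
| Same HFSR hazard, 3.2-month median | 0.00957 | 72.4 days | 25.6% |

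Halving the hazard gives 9.3%, that is 34 × 0.093 = 3.2 expected cases. This is a different scenario from halving the proportion to 8.5% (2.9 cases). Adding the 30-day window without recalibrating to 17% gives medians of 52.3 days (base) and 56.6 days (halved), the same pattern.

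**Early onset.** Onset lognormal with log-SD 0.6 (assumed), exponential end of observation, 1,000,000 simulated patients, median time on treatment 1.9 to 4.0 months:

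| True median | Observed, no window | Observed, 30-day window |
|---|---|---|
| 14 days | 13.2–13.6 | 13.9 |
| 28 days | 24.9–26.3 | 26.2–27.0 |
| 42 days | 35.4–38.5 | 36.4–39.0 |
| 84 days | 62.6–71.4 | 62.8–71.5 |

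For true medians of 14 and 28 days the shortfall without the window runs from (14−13.6)/14 = 3% to (28−24.9)/28 = 11%. It grows as onset gets later.

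**What the alternative would show.** Cumulative incidence by day t, with leaving observation as a competing event, is [L/(L+M)]·[1−exp(−(L+M)t)]. In the three constant-hazard scenarios, in table order, this gives 5.7%, 2.9% and 6.0% at day 28, and 9.4%, 4.9% and 10.6% at day 56. It roughly halves when the HFSR hazard halves, and moves little with treatment duration.

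**The case against.** The strongest case against is that this is a legitimate descriptive measure with a companion. Onset time among affected patients answers part of the objective, and section 8.3.2 reports the Grade 3 proportion with an interval. In the constant-hazard scenarios that proportion would move from 17% to 9.3% or 25.6%, so prevention would be visible there, if imprecisely. The endpoint has no test and no threshold, and the documents give no historical onset time to compare it with. All of this stands, and it keeps the point minor. What remains is that the proportion has no time axis: the two summaries together do not give the risk by a stated day among all treated patients.

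Three stronger readings are tempting, and the documents do not support them.

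- **HFSR follow-up ends at progression.** Recording runs to 30 days after the last dose, and section 5.2.1 allows study drug beyond progression.
- **The measure reflects time on treatment and not HFSR.** That follows from a constant hazard, which is an assumption. The documents do not give the timing of Grade 3 onset. Section 1.4 says that first symptoms can appear after 5–7 days, photographs are confined to cycle 1 (7.1), and the interim check comes after one cycle (8.6). These lean towards early onset without proving it. Under early onset the measure mostly follows HFSR. The constant-hazard scenario at 3.2 months also predicts 25.6% Grade 3, whereas CONCUR had 16.2% with that PFS; the populations differ, so this is not decisive.
- **The objective cannot be answered at all.** It is answered for affected patients. What is missing is the course of risk in the whole treated group.

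**Conclusion.** The point holds as a limited one. Section 8.4.1 states a rule that conditions on the outcome, truncates onset at the end of adverse-event recording, and leaves about 6 of 34 patients in the summary at the CORRECT rate. It cannot show the time course of Grade 3 risk across all treated patients, and no other planned summary does.

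The counts rest only on 17% and N=34. The size of any distortion by treatment duration rests on the unknown timing of Grade 3: large under a constant hazard (48.0 to 72.4 days with no change in HFSR), about 3–11% if the true median is 14–28 days. Neither case can be taken as the expected one. Severity is minor: a secondary descriptive endpoint, with the primary test and sample size untouched.

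**What to change.** In section 8.4.1:

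1. Define time from first dose to first Grade 3 HFSR for all treated patients.
2. Estimate cumulative incidence by the Aalen-Johansen method. Treat death, and reaching the end of the adverse-event window (30 days after last dose) without Grade 3, as competing events. Censor only patients still under observation at data cut-off.
3. Report the estimate with 95% confidence intervals at fixed times such as the end of cycles 1 and 2, and show later times with the number at risk. With a 1.9-month median, only about 34 × 2^(−112/57.8) = 9 patients would still be on treatment at the end of cycle 4.
4. Keep the event-only times as a descriptive listing.

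The end of the window should not be ordinary censoring. Stopping is often driven by progression and may be informative, and censoring would estimate risk as if observation never ended: 1−exp(−L·56) = 12.8% at day 56 in the base scenario, against 9.4%. With no one censored at cut-off, the recommended estimate is simply the number with Grade 3 by day t divided by all treated, so the curve ends at the crude Grade 3 proportion in the same patients.

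The cost is a change of wording and one figure. Adverse-event start dates (7.1.2.2, 7.5.1.3, 8.5), dosing records (6.7) and on-study death dates (7.1.2.5) are already collected. No visits or patients are added. The downside is a little more analysis and wide intervals, because events will be few.

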8.4.2 Progression-free survival

Progression-free survival is defined as the time (days) from start date of study drugs to date of first documented disease progression (radiological or clinical) or death due to any cause, if death occurs before progression is documented. The actual date that the tumor scan was performed will be used for this calculation. Progression-free survival for patients without disease progression or death at the time of the final analysis will be censored at the last date of tumor evaluation. Progression-free survival for patients who have no tumor assessments after baseline will be censored at 1 day. Missing or non-evaluable tumor assessments will not be taken into account in the calculation of PFS. Every effort will be made to obtain radiologic imaging for documentation of progression. In those cases where patients are unable to obtain radiologic examinations due to deterioration of medical condition, the date of clinical progression will be used for the determination of the date of progression. The PFS distribution will be presented descriptively using Kaplan-Meier curves. The median PFS from the Kaplan-Meier distribution will be determined along with the associated 95% confidence interval.

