The following assessments should be performed on **day 7 of the second cycle** (+/- 3 days):

- Blood pressure
- Assessment of AEs
- Concomitant medications

The following assessments should be performed on **day 14 of the second cycle** (+/- 3 days):

- Physician visit
- ECOG status
- Liver function tests
- Assessment of AEs
- Concomitant medications
- Blood pressure

Tumor measurements (CT/MRI scans) will be conducted every 8 weeks. A PET scan is not acceptable for radiological evaluation. Throughout the study, the identical lesions to those identified and measured at baseline must be evaluated using the same technique, and preferably by the same investigator/radiologist. MRI/CT scans must meet the standard of care for the imaging of lesions in the respective organ system(s). Copies of all imaging (CT scans, MRI, X-rays, ultrasound, photographs of cutaneous lesions, etc.) performed for tumor assessment in all enrolled patients will be stored electronically at the site.

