7.1.2.3 End of Treatment Visit

When a patient is taken off treatment, the following assessments should be performed within 14 days (+/- 7 days) after study treatment has stopped:

- Brief medical history and complete physical examination including review of all organ systems, examination of pertinent organ systems, vital signs (heart rate, blood pressure and temperature) and weight
- ECOG performance status
- A CBC with differential should be performed: RBC, hemoglobin, hematocrit, platelet count and WBC. WBC must include differential neutrophil, lymphocyte, monocyte, basophil and eosinophil counts.
- Liver function tests
- CEA testing
- Creatinine
- Urinalysis: appearance, pH, glucose, ketones, erythrocytes, leukocyte esterase, nitrite, bilirubin, urobilinogen, protein, creatinine, and protein/creatinine ratio. A microscopic analysis should be performed if the appearance is turbid, or if protein, leukocytes, erythrocytes or nitrite are out of normal range.

Phase II Study of Perindopril and Regorafenib in mCRC (PARICCA)

- Quantification of proteinuria by urinary protein/creatinine ratio on a random urine sample preferably taken at mid-morning. This should be reported as the ratio of concentrations of total urine protein (in mg/dl) to urine creatinine (in g/dl).
- Measurement of GFR according to the MDRD (Modified diet in renal disease) abbreviated formula.
- 12-lead ECG
- Concomitant medications
- Toxicity and adverse events documentation
- For patients who discontinue for reasons other than disease progression, tumor measurements and evaluation of tumor response of all measurable lesions should be performed according to RECIST criteria, version 1.1.

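### The day-1 censoring sentence in 8.4.2 is not limited to event-free patients, so read literally it censors unscanned early deaths and clinical progressions that the same section counts as PFS events

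*Combined protocol and SAP*

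**What the plan says.** All the PFS rules are in section 8.4.2 of the combined protocol and SAP.

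- **Event.** PFS runs from the start of study drugs to the first documented progression, radiological or clinical, "or death due to any cause, if death occurs before progression is documented". No post-baseline scan is required for an event.
- **General censoring.** "Progression-free survival for patients without disease progression or death at the time of the final analysis will be censored" at the last tumor evaluation.
- **Day-1 censoring.** The next sentence reads: "Progression-free survival for patients who have no tumor assessments after baseline will be censored at 1 day".
- **Clinical progression.** For patients too unwell to be imaged, "the date of clinical progression will be used for the determination of the date of progression".
- **Output.** "The PFS distribution will be presented descriptively using Kaplan-Meier curves", together with the median and its 95% confidence interval.

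Two provisions elsewhere bear on who could lack a post-baseline scan. Section 7.1.2.2 says: "Tumor measurements (CT/MRI scans) will be conducted every 8 weeks". Section 7.1.2.3 sets the end-of-treatment assessment: "For patients who discontinue for reasons other than disease progression, tumor measurements and evaluation of tumor response of all measurable lesions should be performed".

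**The concern.** The general censoring sentence applies only to patients without progression or death. The day-1 sentence drops that condition, and no order of precedence is given. A patient who dies unscanned in week 5 is therefore an event under the definition and a day-1 censoring under this sentence. The day-1 sentence is also the more specific rule for unscanned patients, so a programmer could reasonably let it override.

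Such patients can arise. The first on-treatment scan is due at about day 56, and the end-of-treatment tumor assessment is not requested of a patient who stops because of progression, including clinical progression. These would be among the earliest failures, so censoring them at day 1 is informative. The reported median would be biased upward, which is the direction of the benefit that section 1.5 hopes for.

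**Working it through.** **1. The rules side by side.** The documents give no PFS sample size, event count or target, so there is no stated figure to reproduce. The check is of the text.

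| Patient with no post-baseline scan | Event definition | Day-1 sentence as written |
|---|---|---|
| Dies in week 5 | Event at date of death | Censored at day 1 |
| Clinical progression in week 5 | Event at that date | Censored at day 1 |
| No event | Not an event | Censored at day 1 |

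Only the last row is consistent.

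**2. Inputs for size.** N = 34 (section 8.7). First on-treatment scan at day 56 (8 weeks, section 7.1.2.2). Reference medians are from section 1.6: for CORRECT, "PFS was 1.9 vs 1.7 months", regorafenib first; for CONCUR, 3.2 months on regorafenib. With a month of 30.4375 days these are 1.9 × 30.4375 = 57.8 days and 3.2 × 30.4375 = 97.4 days. Exponential event times are an assumption.

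**3. How much falls before the first scan.** P(event by day 56) = 1 − 2^(−56/m), where m is the median in days. This gives 49% at m = 57.8 and 33% at m = 97.4. It covers all PFS events, not only the unscanned ones.

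**4. Shift per affected patient.** Suppose k of 34 patients fail before day 56 and are censored at day 1. From then on 34 − k are at risk. The literal curve reaches one half when the true survival is 0.5 × (34 − k)/34, so

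shift in median = m × log2(34/(34 − k)).

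This is a large-sample result with no scan grid. It holds when the affected failures precede the median, as they do here because day 56 comes before both medians.

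| k | m = 57.8 days | m = 97.4 days |
|---|---|---|
| 1 | +2.5 | +4.2 |
| 2 | +5.1 | +8.5 |
| 4 | +10.4 | +17.6 |
| 6 | – | +27.3 |
| 8 | +22.4 | – |

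Per patient this is 2.5 to 2.8 days (22.4/8 = 2.8) at 1.9 months, and 4.2 to 4.6 days (27.3/6 ≈ 4.6) at 3.2 months.

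**5. Scale.** In simulated trials of 34 patients without a scan grid, the typical log-log 95% confidence interval for the median was about 31 to 90 days at 1.9 months and 52 to 152 days at 3.2 months.

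**6. With the 8-week grid, at 1.9 months.** Scan-detected progressions were moved to the next scan date; deaths and clinical progressions kept their own dates. Assume that a share of all events are deaths or clinical progressions, and that every one of these before day 56 is unscanned. At a 5% share (0.8 patients affected on average) the median rose in 11% of trials, with a mean shift of +4.5 days. At 20% (3.3 patients) it rose in 47%, with a mean of +14.6 days. So with few affected patients the median often does not move. When it does, it moves in larger steps (4.5/0.11 ≈ 41 days; 14.6/0.47 ≈ 31 days), because scan-detected events fall only on scan dates. If only half of those patients are unscanned, the mean shifts fall to +2.6 and +8.2 days. The shares are assumptions.

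**The case against.** The strongest reply is that section 8.4.2 already makes the meaning plain. It defines the event and then censors event-free patients at their last tumor evaluation. That rule leaves no usable date for an event-free patient with no evaluation after baseline, and the day-1 sentence supplies one. In sequence it reads as a sub-case. The literal reading would also defeat the clinical-progression sentence for anyone who deteriorates before the first scan. For deaths, both the event definition and the preceding censoring sentence point the same way. This stands as to intent. It does not remove the conflict in the wording.

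The reply also holds that few patients can be affected, and this too largely stands. Section 8.4.2 asks for every effort to image progression. Section 7.3 asks for imaging at the defined timepoints and a radiological assessment soon after stopping before progression. Appendix 14.1 asks for objective progression to be documented even after treatment stops for symptomatic deterioration. Section 5.1.1 requires a life expectancy of at least 3 months and ECOG 0 or 1, which makes death before day 56 less likely. These limit the number but do not bring it to zero.

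A reader might go further and infer that the plan means to discard early deaths, or that the reported median will be inflated by weeks. The documents support neither. The first runs against three neighbouring sentences. The second needs a share of clinical or fatal events and an unscanned fraction that the documents do not give. Nor should the wording on patients being off study after the 30-day visit (sections 2.1 and 7.1.2.5) be read as adding to this point. It is a separate, minor clarification.

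**Conclusion.** The point holds as a defect of wording. As written, the day-1 sentence contradicts the event definition for patients who die or progress clinically without a post-baseline scan, and applying it would bias the median PFS upward. The intended rule can be inferred with fair confidence, but an analyst should not have to infer it.

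The likely effect is modest. The per-patient shift rests on exponential times, a large-sample approximation and no scan grid, and the number of affected patients is unknown. In the simulations at 1.9 months without a grid, with all early deaths and clinical progressions unscanned, the shifted median stayed below the unshifted upper confidence limit in at least 99% of trials for assumed shares up to 30%.

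PFS is secondary and descriptive, and no test of it is planned. The primary HFSR comparison, its 5% level, its 80% power and N = 34 do not depend on it. The correction is worth making but is not critical to the trial.

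**What to change.** In section 8.4.2, limit the day-1 sentence to event-free patients. After the reference to patients with no tumor assessments after baseline, insert: *and no documented progression (radiological or clinical) or death*. The sentence then censors at 1 day only those who have neither a post-baseline assessment nor an event. Leave the other PFS event and censoring rules unchanged.

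The cost is one clause. It needs no new data, visits or patients and has no effect on the primary analysis. It should be settled before the PFS analysis is programmed.
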